8.2. Safety Assessments

Planned time points for all safety assessments are provided in the SoA.

8.2.1. Physical Examinations, Clinical Signs and Symptoms

A complete physical examination and medical history (including preexisting clinical signs and symptoms) will be performed at the screening visit. This examination excludes pelvic, rectal, and breast examinations unless clinically indicated.

A symptom-directed physical examination will be performed at other visits, as specified in the SoA and as clinically indicated.

Investigators should pay special attention to clinical signs related to COVID-19, to ongoing medical conditions and to previous serious illnesses.

8.2.2. Vital Signs

Vital signs will be measured at rest as specified in the SoA. Vital signs include

- body temperature
- blood pressure

- pulse rate
- respiration rate
- saturation of peripheral oxygen, and
- supplemental oxygen flow rate, FiO₂ if known, and method of delivery, if applicable.

If available during the study, optional remote vital status monitoring may be used to obtain vital data.

Additional vital signs may be measured during the study if warranted, as determined by the investigator.

8.2.3. Clinical Safety Laboratory Assessments

See Section 10.2, Appendix 2 for the list of clinical laboratory tests to be performed and the SoA for the timing and frequency. All protocol-required laboratory assessments, as defined in Appendix 2, must be conducted in accordance with the laboratory manual and the SoA.

Clinically significant abnormal laboratory findings are those which are not associated with the underlying disease, unless judged by the investigator to be more severe than expected for the participant's condition.

All laboratory tests with values considered clinically significantly abnormal during participation in the study or within 28 days after the dose of study intervention should be repeated until the values return to normal or baseline or are no longer considered clinically significant by the investigator or sponsor.

If such values do not return to normal/baseline within a period of time judged reasonable by the investigator, the etiology should be identified and the sponsor notified.

The investigator must review the laboratory results, document this review, and record any clinically relevant changes occurring during the study in the CRF.

The laboratory reports must be filed with the source documents.

If laboratory values from non-protocol specified laboratory assessments performed at a local laboratory that require a change in participant management or are considered clinically significant by the investigator (i.e., SAE or AE), then the AE or SAE will be recorded by the investigator in the CRF.

Pregnancy Testing

Women of childbearing potential (WOCBP) must undergo pregnancy testing according to the SoA.

8.2.4. Hospitalization events

If a participant is admitted to the hospital, the participant will remain in the study and follow the procedures outlined in the SoA. Hospitalization is defined as ≥ 24 hours of acute care.

The date of hospitalization events will be recorded in the CRF and includes

- hospitalization
- emergency room visit
- intensive care unit admittance

- extended care facility admittance, and
- discharge for any of the above.

8.2.5. Procedures of Special Interest

In hospitalized participants, clinical status and concomitant procedures of special interest will be recorded in the CRF and include consciousness status using alert, confusion, verbal, pain, unresponsive scale (ACVPU), limitation on activities due to COVID-19 and requirements for:

- ongoing hospital medical care
- supplemental oxygen
- non-invasive ventilation or a high flow oxygen device
- mechanical ventilation
- extracorporeal membrane oxygenation, or
- additional organ support (e.g. pressors, renal replacement).

8.3. Adverse Events and Serious Adverse Events

Adverse events will be reported by the participant (or, when appropriate, by a caregiver, surrogate, or the participant's legally authorized representative).

The investigator and any qualified designees are responsible for detecting, documenting, and recording events that meet the definition of an AE or SAE and remain responsible for following up AEs that are serious, considered related to the study intervention or study procedures, or that caused the participant to discontinue the study intervention or study (see Section 7).

8.3.1. Time Period and Frequency for Collecting AE and SAE Information

All AEs and SAEs will be collected from the time of signing of the ICF until participation in study has ended.

Adverse events that begin before the start of study intervention but after signing of the ICF will be recorded on the Adverse Event CRF.

Although all AEs after signing the ICF are recorded by the site in the CRF/electronic data entry, SAE reporting to sponsor within the required timeframe begins after the participant has signed the ICF and has received study drug. However, if an SAE occurs after signing the ICF, but prior to receiving study intervention, it needs to be reported within the required timeframe ONLY if it is considered reasonably possibly related to study procedures.

All SAEs will be recorded and reported to the sponsor or designee immediately and under no circumstance should this exceed 24 hours, as indicated in Section 10.3.4, Appendix 3. The investigator will submit any updated SAE data to the sponsor within 24 hours of it being available.

Investigators are not obligated to actively seek AEs or SAEs after conclusion of the study participation. However, if the investigator learns of any SAE, including a death, at any time after a participant has been discharged from the study, and he/she considers the event to be reasonably related to the study intervention or study participation, the investigator must promptly notify the sponsor.

8.3.2. Method of Detecting AEs and SAEs

The method of recording, evaluating, and assessing causality of AE and SAE and the procedures for completing and transmitting SAE reports are provided in Section 10.3, Appendix 3.

Care will be taken not to introduce bias when detecting AEs and/or SAEs. Open-ended and non-leading verbal questioning of the participant is the preferred method to inquire about AE occurrences.

8.3.3. Follow-up of AEs and SAEs

After the initial AE/SAE report, the investigator is required to proactively follow each participant at subsequent visits/contacts. All SAEs will be followed until resolution, stabilization, the event is otherwise explained, or the participant is lost to follow-up (as defined in Section 7.3). Further information on follow-up procedures is provided in Section 10.3, Appendix 3.

8.3.4. Regulatory Reporting Requirements for SAEs

Prompt notification by the investigator to the sponsor of a SAE is essential so that legal obligations and ethical responsibilities towards the safety of participants and the safety of a study intervention under clinical investigation are met.

The sponsor has a legal responsibility to notify both the local regulatory authority and other regulatory agencies about the safety of a study intervention under clinical investigation. The sponsor will comply with country-specific regulatory requirements relating to safety reporting to the regulatory authority, Institutional Review Boards (IRB)/Independent Ethics Committees (IEC), and investigators.

An investigator who receives an investigator safety report describing a SAE or other specific safety information (e.g., summary or listing of SAEs) from the sponsor will review and then file it with the IB and will notify the IRB/IEC, if appropriate according to local requirements.

8.3.5. Pregnancy

Although normal pregnancy is not an adverse event, details of all pregnancies in female participants will be collected for 90 days after dosing.

If a pregnancy is reported, the investigator should inform the sponsor within 24 hours of learning of the pregnancy and should follow the procedures outlined in Section 10.4.3, Appendix 4.

Abnormal pregnancy outcomes, for example, spontaneous abortion, fetal death, stillbirth, congenital anomalies, and ectopic pregnancy, are considered SAEs.

8.3.6. Hypersensitivity Reactions

Biologic agents carry the risk of systemic hypersensitivity reactions.

If such a reaction occurs, additional details describing each symptom should be provided to the sponsor in the infusion-related reaction/hypersensitivity CRF.

If symptoms and/or signs occur during or within 6 hours after infusion of LY3819253 and are believed to be hypersensitivity or due to cytokine release, then investigators are encouraged to

report the event as infusion-related immediate hypersensitivity reaction or cytokine release-associated infusion reaction, respectively.

Sites should have appropriately trained medical staff and appropriate medical equipment available when study participants are receiving intervention. It is recommended that participants who experience a systemic hypersensitivity reaction be treated per the local standard of care.

In the case of generalized urticaria or anaphylaxis, additional blood and urine samples should be collected as described in Section 10.6, Appendix 6, "Recommended Laboratory Testing for Hypersensitivity Events". Laboratory results are provided to the sponsor via the central laboratory.

In case of skin lesions or rash consistent with vasculitis, efforts should be made to perform the following as soon as possible

- dermatology consultation
- skin biopsy, and
- photographs of lesions of interest, including skin biopsy site.

8.3.7. Infusion-related Reactions

As with other mAbs, infusion-related reactions may occur during or following LY3819253 administration. If an infusion-related reaction occurs, additional data describing each symptom and sign should be provided to the sponsor in the CRF.

This table describes the location of infusion-related reaction information in this protocol.

Topic	Location
Special treatment considerations	Section 6.1.1
Premedication for infusions	Section 6.1.1.1
Management of infusion reactions	Section 6.1.1.2
DAIDS table describing severity	Section 6.1.1.2
Treatment guidelines for infusion-related reactions	Section 6.1.1.2

Abbreviation: DAIDS = Division of AIDS.

Symptoms occurring during or after infusion of study intervention may also be defined according to AE categories such as acute allergic reaction or cytokine release syndrome (DAIDS 2017).

8.3.8. Product Complaints

A product complaint is any written, electronic, or oral communication that alleges deficiencies related to the identity, quality, durability, reliability, safety, effectiveness or performance of a trial intervention.

Sponsor collects product complaints on study intervention and drug delivery systems used in clinical studies in order to ensure the safety of study participants, monitor quality, and to facilitate process and product improvements.

Participants or participant's legal authorized representative will be instructed to contact the investigator as soon as possible if they have a complaint or problem with the intervention so that the situation can be assessed.

NOTE: AEs/SAEs that are associated with a product complaint will also follow the processes outlined in Section 8.3.3 and Section 10.3, Appendix 3, of the protocol.

Time Period for Detecting Product Complaints

Product complaints that result in an adverse event will be detected, documented, and reported to the sponsor during all periods of the study in which the intervention is used.

If the investigator learns of any product complaint at any time after a participant has been discharged from the study, and such incident is considered reasonably related to an intervention provided for the study, the investigator will promptly notify the sponsor.

Prompt Reporting of Product Complaints to Sponsor

Product complaints will be reported to the sponsor within 24 hours after the investigator becomes aware of the complaint.

The Product Complaint Form will be sent to the sponsor by a method designated by the sponsor.

Follow-up of Product Complaints

Follow-up applies to all participants, including those who discontinue study intervention.

The investigator is responsible for ensuring that follow-up includes any supplemental investigations as indicated to elucidate the nature and/or causality of the product complaint.

New or updated information will be recorded on the originally completed form with all changes signed and dated by the investigator and submitted to the sponsor.

8.4. Treatment of Overdose

There is no known antidote for an overdose of LY3819253 alone or in combination with LY3832479.

In the event of an overdose, the investigator should

1. contact the sponsor immediately.
2. closely monitor the participant for any AE/SAE and laboratory abnormalities
3. provide supportive care as necessary, and
4. document the quantity of the excess dose in the CRF.

Decisions regarding infusion interruptions or modifications will be made by the investigator, in consultation with the sponsor, based on the clinical evaluation of the participant.

8.5. Pharmacokinetics

Venous blood samples will be collected as specified in the SoA for determination of concentrations of LY3819253 and LY3832479 used to evaluate the PK for LY3819253 and LY3832479.

A maximum of 3 samples may be collected at additional time points during the study if warranted and agreed upon between the investigator and the sponsor.

Instructions for the collection and handling of biological samples will be provided by Lilly.

Site staff will record

- the date and time (24-hour clock time) of administration (start and end of infusion), and
- the date and time (24-hour clock time) of each PK sample.

It is essential that the times are recorded accurately.

8.5.1. Bioanalytical

Samples will be analyzed at a laboratory approved by the sponsor and stored at a facility designated by the sponsor. Concentrations of LY3819253 and LY3832479 will be assayed using a validated bioanalytical method. Analyses of samples collected from placebo-treated participants are not planned.

Sample retention is described in Section [10.1.12](#), Appendix 1. Remaining samples used for PK may be pooled and used for exploratory metabolism or bioanalytical method experiments as deemed appropriate.

8.6. Pharmacodynamics

The SARS-CoV-2 viral RNA level and viral clearance will be evaluated by nasopharyngeal and/or mid-turbinate, nasal, or oropharyngeal swabs. See Section [10.2](#), Appendix 2; and Section [1.3](#), the SoA, for sample collection information.

Sample retention is described in Section [10.1.12](#), Appendix 1. Remaining samples may be used for additional exploratory studies to better understand LY3819253 alone and in combination with LY3832479, and the disease, which may include sequencing and/or culture of the virus for future studies.

8.7. Genetics

A whole blood sample will be collected for pharmacogenetic analysis where local regulations allow.

See Section [10.2](#), Appendix 2, and Section [1.3](#), the SoA, for sample collection information.

See Section [10.5](#), Appendix 5, for genetic research, custody, and sample retention information.

8.8. Biomarkers

Blood samples will be collected from all participants for analysis of immune system-related markers. Serum, whole blood for cellular and/or epigenetic analysis, and whole blood RNA samples for exploratory biomarker research will be collected at the time specified in the SoA where local regulations allow.

Samples will be stored and analysis may be performed on biomarkers thought to play a role in immune system related responses to viral infection including, but not limited to, immune pathways, cellular composition, serum analytes, or epigenetic biomarkers, to evaluate their association with observed clinical responses to LY3819253 alone and in combination with LY3832479, and the disease state.

Samples may be used for research to develop methods, assays, prognostics and/or companion diagnostics related to the intervention target (S protein), the COVID-19 disease state, pathways associated with disease, and/or the mechanism of action of the study intervention.

Sample retention is described in Section [10.1.12](#), Appendix 1.

8.9. Immunogenicity Assessments

Visits and times

At the visits and times specified in the SoA, venous blood samples will be collected to determine antibody production against LY3819253 and/or LY3832479. The actual date and time (24-hour clock time) of each sample collection will be recorded.

Sample collection, handling, and use

Instructions for the collection and handling of blood samples will be provided by the sponsor.

Immunogenicity may be assessed by a validated assay designed to detect antidrug antibodies (ADAs) in the presence of LY3819253 and/or LY3832479 at a laboratory approved by the sponsor. Antibodies may be further characterized for their ability to neutralize the activity of LY3819253 and/or LY3832479.

Sample retention

Sample retention is described in Section [10.1.12](#), Appendix 1.

8.10. Health Economics

This section is not applicable for this study.

9. Statistical Considerations

9.1. Statistical Hypotheses

This study will compare LY3819253, alone and in combination with LY3832479, versus placebo in residents and facility staff of skilled nursing and assisted living facilities with a high risk of SARS-CoV-2 exposure. The primary study objective is to demonstrate superior efficacy of LY3819253 alone or in combination with LY3832479 over placebo in the prevention of COVID-19. Efficacy comparisons will be made without regard to changes to any background therapies. A graphical testing sequence strategy will be used to adjust for multiplicity in the primary and key secondary endpoints within Part 1 and Part 2 of the study. All analyses on Part 3 are considered exploratory.

9.2. Sample Size Determination

For Part 1, an estimated 33 events are needed to show superiority of LY3819253 4200 mg over placebo in each of the primary and key secondary endpoints, using the formula by Schoenfeld (1983). An average sample size of approximately 1300 participants who are SARS-CoV-2 PCR negative and serology negative at baseline is expected to obtain the needed number of events for each endpoint.

For Part 2, an estimated 56 events in the Prevention Cohort are needed to show superiority over placebo for either LY3819253 700 mg or LY3819253 350 mg+LY3832479 700 mg in each of the primary and key secondary endpoints. Approximately 2000 participants on average will be randomly assigned to study intervention such that approximately 1700 participants are randomized in the Prevention Cohort with the goal of achieving approximately 56 events on each of the primary and key secondary endpoints.

Due to the dynamic nature of the pandemic, Part 3 will enroll at least 30 participants and up to approximately 500 participants randomized to either LY3819253 700 mg or LY3819253 700 mg + LY3832479 1400 mg. Part 3 of the study is considered exploratory and is not powered for inference between the two treatment arms.

The maximum sample size for this study is approximately 5000 participants in the intent-to-treat (ITT) population.

Participants will be residents and staff of skilled nursing and assisted living facilities. Globally, there are many reports of the rapid spread of COVID-19 amongst residents of skilled nursing facilities following identification of an index case, with high associated rates of morbidity and mortality (Arons et al. 2020; Grabowski). Given that residents at these facilities are at higher risk for having a more severe disease course of COVID-19, this will be an important population to participate in the study. Therefore, a minimum of 300 residents will be enrolled.

Operationally, this will be accomplished, when possible, by identifying facilities where approximately half of the participants interested in the study are residents.

For sample size determination for Part 1, the following assumptions were used:

- 1) two-sided significance level of 0.05;
- 2) 90% power for the primary and key secondary endpoints;
- 3) an 8-week placebo group event rate of 4.0% for moderate or worse severity COVID-19;

4) a risk ratio of 0.33 between LY3819253 and placebo in terms of the primary and key secondary endpoints.

For sample size determination for Part 2, the following assumptions were used:

- 1) two-sided significance level of 0.025;
- 2) 90% power for the primary and key secondary endpoints;
- 3) an 8-week placebo group event rate of 5.3% for moderate or worse severity COVID-19;
- 4) a risk ratio of 0.33 between active drug and placebo in terms of the primary and key secondary endpoints.

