Part 3 objectives are exploratory and therefore described in [Section 3](#).

Overall Design

Study J2X-MC-PYAD is a randomized, double-blind, placebo-controlled, prophylaxis study to evaluate the efficacy and safety of intravenous LY3819253, alone and in combination with LY3832479, in preventing SARS-CoV-2 infection and COVID-19, compared to placebo. An independent Data Safety Monitor Board (DSMB) will actively monitor interim data to make recommendations about early study closure or changes to sample size.

Disclosure Statement: This is a three-part, 9-arm interventional study that is double-blinded.

Number of Participants:

For Part 1, a total of approximately 1700 participants (intent-to-treat [ITT] population) will be randomly assigned to study intervention such that approximately 1300 SARS-CoV-2 RT-PCR and serology negative participants are randomized in the study with the goal of achieving approximately 33 events (in each of the primary and key secondary endpoints) in the prevention population.

For Part 2, a total of approximately 2000 participants will be randomly assigned to study intervention based on rapid point of care (POC) testing such that approximately 1700 participants SARS-CoV-2 RT-PCR and serology negative participants are randomized in the Prevention Cohort with the goal of achieving approximately 56 events on each of the primary and key secondary endpoints.

Part 3 will enroll at least 30 participants and up to approximately 500 participants randomized to study intervention.

The maximum sample size for this study is approximately 5000 participants in the ITT population.

Intervention Groups and Duration:

Participants will receive one intravenous infusion of study intervention.

The maximum total duration of study participation for each participant of the prevention groups is 24 weeks.

The maximum total duration of study participation for each participant of the treatment group is 12 weeks.

Part 1:

Eligible participants will be randomized to one of two arms: placebo or LY3819253 4200 mg.

Participants will continue to enroll to Part 1 until the needed events for the primary and key secondary endpoints are achieved and the minimum number of residents enroll.

The evaluation period for Part 1 is 8 weeks, with follow-up to 24 weeks.

Part 2:

The Sponsor will decide when to trigger activation of Part 2. Activation of Part 2 will be communicated to sites.

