6.3. Measures to Minimize Bias: Randomization and Blinding

Randomization

Participants who meet all criteria for enrollment will be randomized on Day 1 as follows:

- In Part 1, 1:1 to double-blind treatment
- In Part 2, will be allocated as follows:
 - Prevention Cohort: 1:1:1 to double blinded treatment
 - Treatment Cohort: 1:1, as described in Part 2 Treatment Cohort below
- In Part 3, 1:1 to open label treatment

To achieve between-group comparability, block randomization within each facility will be used. Randomized participants within the facility will be stratified by role within the facility (resident versus facility staff), by sex, and whether or not the participant received a SARS-CoV-2 vaccine prior to screening (in Part 3 only).

All participants will be centrally randomized to study intervention using an Interactive Web Response System (IWRS). Before the study is initiated, the log in information and directions for the IWRS will be provided to each site.

Blinding

Part 1 and Part 2 Prevention Cohort

Part 1 and Part 2 are blinded. Neither participants, nor investigators, nor the sponsor study team will be aware of treatment assignments prior to the final database locks at the conclusion of the study, except as described in the following note.

Note: It is possible that some participants will have the SARS-CoV-2 negative result on the screening point of care test, but could be positive on the baseline SARS-CoV-2 PCR test. The results from the baseline PCR test will not be available until after the participant is randomized. Once positive results are known from the baseline PCR test, these participants will be unblinded and have the option to continue to be followed for safety according to the Prevention Cohort SoA. This table describes general procedures for unblinding.

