9.3. Populations for Analyses

The following populations are defined:

Population	Description
Entered	All participants who provide informed consent.
Enrolled/ITT	All participants assigned to treatment, regardless of whether they take any doses of study treatment, or if they took the correct treatment. Participants will be analyzed according to the treatment group to which they were assigned.
Facility Staff	All participants in the Enrolled/ITT population who are staff/employees of the facility.
Residents	All participants in the Enrolled/ITT population who are residents of the facility.
Part 1 Safety	All participants randomly assigned to study intervention in Part 1 and who take at least 1 dose of study intervention. Participants will be analyzed according to the intervention they actually received.
Part 2 Safety	All participants randomly assigned to study intervention in Part 2 and who take at least 1 dose of study intervention. Participants will be analyzed according to the intervention they actually received.
Part 3 Safety	All participants randomly assigned to study intervention in Part 3 and who take at least 1 dose of study intervention. Participants will be analyzed according to the intervention they actually received.
Fully Dosed	All participants in the Safety population who receive a complete infusion of study intervention.
Part 1 Prevention	All participants in the Enrolled/Intent-to-Treat population in Part 1 who are SARS-CoV-2 RT-PCR negative and serology negative at baseline.

Population	Description
Part 1 Treatment	All participants in the Enrolled/ITT population in Part 1 who are SARS-CoV-2 RT-PCR positive at baseline and serology negative.
Part 2 Prevention	All participants in the Enrolled/Intent-to-Treat population in the Prevention Cohort in Part 2 who are SARS-CoV-2 POC and RT-PCR negative and serology negative at baseline.
Part 2 Treatment	All participants in the Enrolled/ITT population in the Treatment Cohort in Part 2 who are SARS-CoV-2 POC and RT-PCR positive and serology negative at baseline.
Part 3 Treatment	All participants in the Enrolled/ITT population in Part 3 who are SARS-CoV-2 RT-PCR positive and serology negative at baseline.
Serology-Positive	All participants in the Enrolled/ITT population who are SARS-CoV-2 serology positive at baseline.
POC-Positive/RT-PCR Negative	All participants in the Enrolled/ITT population in Part 2 who are SARS-CoV-2 POC positive and RT-PCR negative at baseline.

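### Part 2 planning figures disagree: at the stated rates, about 1700 baseline-negative participants yield about 50 moderate-or-worse events, not the 56 that trigger the lock, and the planning alpha of 0.025 is not a Part 2 test level

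*Protocol*

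**What the plan says.** Protocol 9.2 and SAP 5.2 give the Part 2 target as "approximately 1700 participants are randomized in the Prevention Cohort with the goal of achieving approximately 56 events" on each primary and key secondary endpoint. The assumptions are a "two-sided significance level of 0.025", 90% power, "an 8-week placebo group event rate of 5.3% for moderate or worse severity COVID-19", and "a risk ratio of 0.33 between active drug and placebo in terms of the primary and key secondary endpoints". Protocol 6.3 sets the allocation: "Prevention Cohort: 1:1:1 to double blinded treatment".

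The synopsis defines the 1700 more narrowly: "approximately 1700 participants SARS-CoV-2 RT-PCR and serology negative participants are randomized in the Prevention Cohort". That agrees with the Part 2 Prevention population in Protocol 9.3, which takes those "who are SARS-CoV-2 POC and RT-PCR negative and serology negative at baseline". Protocol 9.2 and SAP 5.2 do not put that condition on the 1700.

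SAP 6.1.5.2 triggers the Part 2 primary lock when 56 members of the Part 2 Prevention population have had a moderate or worse case. SAP 6.1.4 sets an experiment-wise error rate of 0.05 for each part. SAP 6.5 tests the combination arm first: the primary endpoint at 0.05 and, if it succeeds, moderate-or-worse COVID-19 at 0.04 and infection at 0.01, with either one rising to 0.05 if the other succeeds. The same scheme is run for monotherapy only if all three combination endpoints succeed. Schoenfeld's formula is named for Part 1; no method is named for Part 2.

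**The concern.** A sample size, an event target, event rates, an alpha and a power should describe one design. Here the number of participants and the number of events, which fix the enrolment forecast and the lock date, do not follow from each other at the plan's own rates. The alpha used for planning also belongs to no test that will be run, so the 90% power statement cannot be attached to any of them. At stake are the enrolment and duration forecast and a reader's ability to say what power the trial has.

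**Working it through.** **Inputs.** Part 2: 1700 participants, 56 events, two-sided alpha 0.025, power 90%, placebo rate 0.053, risk ratio 0.33 (Protocol 9.2, SAP 5.2); allocation 1:1:1 (Protocol 6.3). Part 1: 1300 participants, 33 events, alpha 0.05, power 90%, placebo rate 0.04, risk ratio 0.33, allocation 1:1.

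**1. Calibration on Part 1.**
- Expected events: 650 × 0.04 × 1.33 = 34.6.
- Schoenfeld, 4 × (1.960 + 1.2816)² / (ln HR)²: 34.2 with 0.33 used as the hazard ratio. It is 33.4 after converting the risk ratio to a hazard ratio, ln(1 − 0.04 × 0.33) / ln(1 − 0.04) = 0.3255.
- The plan states 33, so the approach reproduces Part 1 closely.

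**2. Events from 1700 in Part 2.**
- Placebo: 1700/3 × 0.053 = 30.0. Each active arm: 30.0 × 0.33 = 9.9.
- Total: 1700/3 × 0.053 × (1 + 2 × 0.33) = **49.9**, against 56. Shortfall: 6.1/56 = 11%.
- This takes all 1700 as baseline negative, with full 8-week follow-up and no dropout; relaxing any of these lowers the count.
- Getting 56 from 1700 would need a placebo rate of 56 / (1700/3 × 1.66) = 5.95%, or an average active-arm risk ratio of (56/30.03 − 1)/2 = 0.43. Neither is stated.

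**3. Events required at the stated alpha and power.** One active arm against placebo, then scaled to three arms by 1.66/1.33:

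| Effect used as hazard ratio | Pair | Three arms |
|---|---|---|
| 0.33 | 40.4 | 50.4 |
| 0.324 = ln(1 − 0.053 × 0.33) / ln(1 − 0.053) | 39.1 | 48.8 |

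So 1700, the rates, 0.025 and 90% agree with one another at about 50 events; 56 does not fit.

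**4. Participants needed for 56 events.** 3 × 56 / (0.053 × 1.66) = 1909.5, about 1910 baseline-negative participants (about 210 more than 1700). At the plan's 1700/2000 ratio that is 1909.5/0.85 = 2246, about 2250 randomized in Part 2. Adding 1700 (Part 1) and 500 (Part 3 maximum) gives about 4450, inside the cap of about 5000.

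**5. Power under SAP 6.5.** Assume 56 events on each endpoint and risk ratio 0.33. The pair then has d = 56 × 1.33/1.66 = 44.87 events, and the test statistic has mean |ln 0.33| × √44.87 / 2 = 3.713.
- Single tests: 96.0% at 0.05, 95.1% at 0.04, 92.9% at 0.025, 87.2% at 0.01.
- Whole scheme, simulated with assumed correlations of 0 to 0.8 between the three test statistics: infection 94 to 96% once recycling is applied, before the primary gate. Including the gate, infection is 92 to 93% and moderate-or-worse 92 to 94%. All three combination endpoints succeed in 88 to 92%.

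**The case against.** The best defence is that little turns on this. The lock counts events, sizes are given as approximate or average, the DSMB may recommend changes to sample size, and "The maximum sample size for this study is approximately 5000 participants". If about 50 events suffice, waiting for 56 adds power. Sizing at a stricter alpha than the eventual test is legitimate, and Protocol 9.4.6 leaves the final sequence to the SAP. All of this stands, and it limits the consequence. It does not make 1700 yield 56, and approximate wording does not cover the gap, since Part 1 uses similar wording and does reproduce.

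Four stronger readings are tempting and are not supported.
- **The infection endpoint has only 87% power.** That is the first-step figure at 0.01. It ignores the rise to 0.05 when moderate-or-worse succeeds, and it assumes 56 infection events, although the plan gives no 4-week infection rate.
- **1700 is the wrong number.** The documents do not show which figure is in error; 1700 agrees with the stated alpha, power and rates, and 56 is the one that stands apart.
- **The trial would probably miss its target.** If enrolment stopped at 1700, the chance of 56 or more events would be about 21%, but the plan has no such stop.
- **The 56 came from a split of alpha.** Schoenfeld at two-sided 0.0125 with hazard ratio 0.324 gives 56.1 events over three arms, but the plan states no such split, so this cannot be taken as the source.

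**Conclusion.** The inconsistency is real. At the stated allocation and rates, 1700 baseline-negative participants yield 49.9 moderate-or-worse events against a stated and lock-triggering 56, and 56 events would need about 1910. The stated alpha and power require 48.8 to 50.4 events, assuming that Schoenfeld's formula was meant for Part 2 as well. The level 0.025 is not used by any Part 2 test in SAP 6.5.

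If the 56-event lock and the stated rates hold, expected enrolment or time to lock is understated, by about 210 negative participants if it is met through enrolment. A reader might infer inflated Type I error or an invalid analysis. Neither follows: SAP 6.5 sets the tests without reference to 0.025, that level is stricter than the levels for the primary and moderate-or-worse tests, and the lock waits for its events. The power figures rest on 56 events per endpoint, risk ratio 0.33 and the assumed correlations; monotherapy power is further conditional on success of all three combination endpoints.

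**What to change.** Reconcile the synopsis, Protocol 9.2 and SAP 5.2, choosing the route that matches how the design was derived:

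- If the 56-event lock is kept and the rates are right, restate the expected size as about 1910 RT-PCR- and serology-negative participants, about 2250 randomized in Part 2.
- If a different placebo rate or risk ratio was used, correct that figure.
- If 1700 and the stated assumptions are right, restate the required events as about 50 and change the trigger in SAP 6.1.5.2 to match.

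In every case, carry the synopsis definition of the 1700 into Protocol 9.2 and SAP 5.2, and state the method, effect measure and alpha behind 56 and 0.025. Replace the single 90% statement with power under the SAP 6.5 scheme, including the primary gate and recycling. At 56 events per endpoint that is about 96% for the primary and 92 to 94% for each key secondary, with monotherapy reported as conditional on all three combination endpoints (about 88 to 92%). State the assumed 4-week infection rate so that the infection figure can be checked.

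The cost is wording and a short recalculation. Keeping 56 adds no participants beyond those the lock already implies at the stated rates; only the third route alters a trigger.
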